
**Fig. 4. Power Calculations for (A)** Mean difference in  $\Delta$  in Body Image Scale scores between baseline and 1-month post intervention, comparing BRIGHT and AC; **(B)** standardized effect, comparing  $\Delta$  in Body Image Scale scores between BRIGHT and AC from baseline to 1-month post intervention

early stage of development (single-site pilot RCT) to ensure follow-up on promising interventions to guide and power a subsequent larger RCT to fully evaluate the efficacy of BRIGHT as a treatment of BID in HNC survivors (i.e. test BRIGHT with significance level of 0.05). We therefore consider our RCT to be appropriately and rigorously designed to detect a clinically meaningful reduction in BID.

In order to have 44 patients eligible for the efficacy analysis in the modified ITT population (see **Section 9.3, Population for Analyses**), we plan to enroll 52 patients. Our sample size is inflated by 20% based on interim accrual data. This inflation account for study dropout and the predictable subset of patients would be enrolled in the study, be randomized to BRIGHT or AC, receive a portion or all of the intervention and then subsequently are withdrawn from the study and non-evaluable due to a major HNC surgery or recurrent or second primary cancer.

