Every effort will be made to minimize missing data and lost-to-follow-up participants. Participants will complete assessments at baseline, 1-week post-intervention, 1-month post-intervention, and 3-months post intervention using an iPad-based REDCap collection method. The program coordinator will attempt to contact patients at least three times using a variety of methods of communication (e.g. text message, phone call, email, mail, etc.) to complete outcome measures. This method resulted in 100% instrument completion in our single arm pilot study. In the event that missing data do occur, we will address them via standard multiple imputation procedures. As participants will be randomized to treatment, it is unlikely that missing data will produce biased estimates of treatment effect, as observed and unobserved covariates should theoretically be balanced across treatment groups. In general, less than 10% missing data has little impact on study power and does not induce bias regardless of the missing data mechanism^55. If missing data is greater than 10%, it will be imputed using propensity score or Markov Chain Monte Carlo (MCMC) methods. When covariate information is associated with whether the imputed variable values are missing, we will use the propensity score method, which calculates the propensity score from modeling the distribution of the missing indicator variable based on the observed data and then applies an approximate Bayesian bootstrap imputation to each group identified by the propensity score. Otherwise, we will use the MCMC method. The data augmentation will be applied to Bayesian inference with missing data by repeating imputation step (i.e., simulating the missing values based on the observation) and step for exploring the posterior distribution based on the complete sample estimates obtained from the imputation step.

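### The missing-data text in Section 9.2 wrongly rules out bias below 10% missing and, above 10%, does not require propensity-score imputation to be done within arm

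*Combined protocol and SAP*

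**What the plan says.** All the missing-data text is in Section 9.2 (Sample Size Determination). It makes four statements in sequence.

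- Any missing data will be handled by standard multiple imputation. No threshold is attached.
- Randomisation is offered as protection: "As participants will be randomized to treatment, it is unlikely that missing data will produce biased estimates of treatment effect".
- A threshold is introduced: "In general, less than 10% missing data has little impact on study power and does not induce bias regardless of the missing data mechanism".
- Named methods follow only beyond that threshold: "If missing data is greater than 10%, it will be imputed using propensity score" or MCMC.

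The choice between the two methods is also stated: "When covariate information is associated with whether the imputed variable values are missing, we will use the propensity score method"; otherwise MCMC applies. The propensity method has two steps. It fits a model for missingness to whatever data were observed, which gives each patient a score. In the second step it "applies an approximate Bayesian bootstrap imputation to each group identified by the propensity score".

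The section names no imputation variables, does not say whether imputation is done by arm, and plans no missing-data sensitivity analysis. Section 9.4.2 specifies a linear mixed model for change in BIS with arm, time and their interaction, and does not say how imputed data sets enter it.

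On the expected amount of loss, Section 9.2 enrols 52 to have 44 in the modified ITT efficacy analysis ("Our sample size is inflated by 20% based on interim accrual data"), and Section 5.5.2 states 20% attrition.

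**The concern.** Randomisation balances baseline characteristics. It does not balance decisions or events that come later and determine whether a 1-month BIS score exists. In this trial those could differ by arm: it is unblinded, sessions last 60 minutes in BRIGHT and 30 in AC (Section 4.1), attendance is a condition of remaining active (Section 6.4), and non-compliance can lead to discontinuation (Section 7.2). A claim of no bias under every mechanism is therefore wrong in principle.

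Above 10%, the donor groups are defined by the propensity to be missing. A group formed that way can contain both arms. If an AC value fills a BRIGHT gap, or the reverse, the imputed patients carry little or none of the treatment difference, and the primary contrast is pulled towards zero. That matters because Section 9.2 says the trial is meant to guide and power a larger one.

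**Working it through.** **Inputs.** From Section 9.2: 1-month change of 0.2 (SD 5.9) for AC and 4.6 (SD 3.9) for BRIGHT, where positive means improvement; difference 4.6 − 0.2 = 4.4; 22 per arm; two-sided alpha 0.10; standardised effect 0.78; stated power 80.2%.

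**The plan's own figure.** 4.4/5.62 = 0.78. A two-sample t-test with 22 per arm has noncentrality 0.78 × √(22/2) = 2.59 on 42 degrees of freedom, and power 81.6%. This is within 2 points of the stated 80.2%, so the inputs are usable.

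**Below 10%: is bias possible?** If the lowest fraction p of a normal distribution is lost, the observed mean rises by SD × φ(z)/(1 − p), with z the p-quantile.

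- p = 0.08: φ(z)/(1 − p) = 0.1487/0.92 = 0.1616. Losing the worst 8% of BRIGHT changes adds 3.9 × 0.1616 = 0.63. Losing the best 8% of AC changes as well adds 5.9 × 0.1616 = 0.95, total 1.58 (36% of 4.4).
- Milder case: 9% missing overall, all in BRIGHT, so 18% of that arm. If those patients average 2 to 4.4 points worse than the observed BRIGHT patients, the bias is 0.18 × 2 = 0.36 to 0.18 × 4.4 = 0.79.

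One counterexample is enough against a statement that covers all mechanisms. The tail cases are bounds, not forecasts; 8% is about two patients per arm.

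**Above 10%: what if donors are pooled across arms?** Suppose a share m is missing in each arm and the donor groups mix the arms equally. Imputed values then have the same expectation in both arms, so the expected contrast is 4.4 × (1 − m). At 10%, 15% and 20% this gives 3.96, 3.74 and 3.52.

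A simulation checks this: 22 per arm, 1,500 trials per setting, 10 imputations, five propensity groups, approximate Bayesian bootstrap. Missingness depends on one baseline covariate (log-odds slope 0.8 per SD) and not on outcome. The slope, the number of groups and the independence from outcome are assumptions, not figures from the documents. The within-arm row uses the arm itself as the donor group.

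| Donor rule | 10% nominal | 15% | 20% | Attenuation of 4.4 |
|---|---|---|---|---|
| Pooled, arm not in score | 3.92 | 3.69 | 3.54 | 11% to 20% |
| Pooled, arm in score | 4.07 | 3.88 | 3.76 | 7% to 14% |
| Pooled, arm in score and strongly driving missingness | 4.12 | 4.02 | 3.95 | 6% to 10% |
| Within arm | 4.45 | 4.42 | 4.47 | none |

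With pooled donors and arm not in the score, power at two-sided alpha 0.10 is 0.80, 0.75 and 0.69, against 0.87, 0.83 and 0.81 for complete cases in the same data.

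**Could the share exceed 10%?** 52 enrolled for 44 evaluable implies 8/52 = 15.4%; Section 5.5.2 says 20%. Neither figure is necessarily the share to be imputed, as discussed under the objection.

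**The case against.** The strongest reply is that the plan is silent on arm, not wrong about it. A reader might infer that the propensity method ignores arm. The text does not say so: the observed data used for the score could include arm, and imputing each arm separately is not ruled out. With within-arm donors there is no attenuation. This stands, and it makes the second half a gap in specification. It does not remove the point, because arm in the score alone still leaves 6% to 14% attenuation.

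A reader might also infer that, because of the 10% rule, missing data below 10% would go unexamined. That overlooks the sentence promising multiple imputation whenever data are missing; below 10% the section contradicts itself. No sensitivity analysis is planned above 10% either, so its absence cannot be blamed on the threshold.

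Third, 15.4% should not be read as the expected missing share. Section 9.2 lets the enrolment allowance cover patients withdrawn as non-evaluable after major surgery, recurrence or a second primary. If they leave the modified ITT set, they are not imputed. The version history attributes the rise from 48 to 52 to recurrence and second-primary discontinuations; the previous allowance was 4/48 = 8.3%, and the pilot reported complete questionnaires. Section 9.3 counts all randomised patients as evaluable and then lists these subsets without clearly removing them, so a share above 10% remains possible but not established.

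Finally, the sentence begins with *in general*, and attenuation towards zero costs power without creating false positives. Both are fair. The qualifier does not rescue a claim of no bias for every mechanism.

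**Conclusion.** The point holds in two parts of different strength.

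1. Wrong as written: the no-bias claim below 10%, and the reliance on randomisation to prevent bias from missing outcomes. The threshold also conflicts with the unconditional imputation promise. The shifts of 0.63 and 1.58 points are extreme bounds that show bias is possible; they do not show that it is likely.
2. Under-specified: the propensity method above 10%. If donors are pooled across arms, the 4.4-point difference is attenuated by roughly 6% to 20% at about 10% to 20% missing. This requires more than 10% missing, covariates that predict missingness (otherwise MCMC applies) and pooled donors. The sizes rest on the assumed covariate strength, group count and missingness unrelated to outcome.

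The documents do not support saying that the plan will bias its primary result. They leave room for an implementation that would, and they offer a wrong reason for not worrying about it.

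**What to change.** - Delete the sentence that rules out bias below 10%, the sentence that relies on randomisation, and the 10% trigger.
- State one rule for any amount of missing data: the planned linear mixed model (arm, time, arm by time), fitted by likelihood to all available BIS scores in the efficacy population.
- If multiple imputation is kept, impute separately by arm, or with arm in the outcome imputation model, using baseline and all post-baseline BIS scores. This replaces propensity-group donors pooled across arms. State how the imputed data sets feed the mixed model.
- Optional, at low cost: one delta-adjusted sensitivity analysis of the 1-month contrast, since no method that assumes missingness at random can address outcome-related loss.

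The cost is SAP wording and a little programming. No change to sample size or data collection is needed.

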### 9.3 POPULATIONS FOR ANALYSES

Participants will be defined as evaluable for the primary endpoint (change in BIS from baseline to 1-month post-treatment) and thus included in the efficacy analytic population if they are enrolled in the study and randomized. However, there are two subsets of patients (**7.2, Participant Discontinuation/Withdrawal**) for whom the investigator may discontinue participation due to an event or medical condition or situation occurs such that continued collection of follow-up study data would not be in the best interest of the participant or might require an additional treatment that would confound the interpretation of the study. Specifically,

1. Subjects who are enrolled into the study and undergo a significant HNC ablative or reconstructive surgery (defined by a postoperative inpatient stay of at least three days) during the study intervention or follow-up period.
2. Subjects who are enrolled in the study and develop a recurrence of their index HNC (local, regional or distant recurrence, radiologic or biopsy-proven) or metachronous second primary cancer (radiologic or biopsy-proven) during the study intervention or follow-up period.

We will also perform an efficacy analysis on the per-protocol analytic dataset, a subset of the ITT population who completed all 5 intervention (BRIGHT and AC) sessions. These patients are judged to have complied with the protocol sufficiently to ensure that these data would be likely to represent the effects of BRIGHT according to the underlying scientific model.

## 9.4 STATISTICAL ANALYSES

### 9.4.1 GENERAL APPROACH

Graphical displays such as scatterplots and boxplots will be constructed to demonstrate patterns of individual continuous measures and differences between baseline, 1-week, 1- and 3-months post intervention. Summary descriptive statistics (e.g. frequencies and percent for categorical variables, and mean, median, standard deviation, and range for continuous variables) will be reported. For inferential tests, we will use a p-value of 0.05, two-sided, and 95% confidence intervals (CIs) to assess statistical significance (Type I error). Covariates will be pre-specified as described below. Normality of the data will be assessed before underlying statistical procedures will be performed. We will evaluate variable transformations as needed to satisfy assumptions and consider transformations of variables to induce approximate normality and stabilize variance as needed. Nonparametric tests will be applied when appropriate.

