### 9.2 SAMPLE SIZE DETERMINATION

Our primary objective is to compare change in BIS scores from baseline to 1-month intervention between the BRIGHT and AC arms. The primary endpoint is  $\Delta$  in Body Image Scale scores from baseline to 1-month post-intervention. We hypothesize that, compared with patients who receive the AC, patients who receive BRIGHT will have reduced BID as measured by change in BIS scores at 1-month post-intervention relative to baseline. Alternatively, our null hypothesis is that there will be no difference between BRIGHT and AC in terms of improving BID, as measured by change in BIS scores at 1-month post-intervention relative to baseline. All power and sample size calculations were performed using PASS 2008 version 08.0.13. Based on data from our prospective cohort study and single-arm pilot of BRIGHT, we estimate the mean  $\Delta$  in Body Image Scale scores  $\pm$  SD from baseline to 1-month post are  $0.2 \pm 5.9$  and  $4.6 \pm 3.9$  for control and BRIGHT, respectively. This effect size is clinically significant and realistic given results of other psychobehavioral interventions in breast cancer patients with BID. For n=22/arm (proposed sample size), power exceeds 80% for mean difference in change in Body Image Scale scores of at least 3.1 (with SD as large as 4) or mean difference of at least 5.5 (with SD as large as 7) based on two-sided t-test with  $\alpha=0.1$  (**Fig. 4A**). Group sample size of n=22 (AC, BRIGHT) achieved 80.2% power to detect the standardized effect (mean difference in  $\Delta$  Body Image Scale score from baseline to 1-month divided by the pooled SD=5.62) of 0.78 based on the two-sample t-test with two-sided  $\alpha=0.1$  (**Fig 4B**). We will have greater than 90% power for a standardized effect size of 0.93 and greater than 80% power for a standardized effect size of 0.78. These are both considered moderate effect sizes and are feasible for continuous outcomes in the context of variables that are expected to be modulated by the cancer experience. Our power estimate is conservative given our proposed analysis plan using LME regression, which borrows strength over time and is generally more efficient than a t-test. As such we anticipate that smaller effect sizes than described above will be detectable. Our selection of relaxed significance ( $\alpha = 0.1$ ) with maintained power ( $1 - \beta = 0.8$ ) is based on the desire to emphasize power over type I error at this

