### 9.4.2 ANALYSIS OF THE PRIMARY ENDPOINT(S)

Longitudinally measured BIS scores will be modeled using linear mixed effects (LME) regression with the measures at each time point relative to baseline (denoted by  $\Delta$ ) as the response variable and fixed effects for experimental conditions (BRIGHT, AC), time (1-week, 1-month, and 3-months post intervention) and their interaction. Models will include subject-specific random effects to account for correlation among measures obtained from the same subject over time. We will use qq-plots and histograms to investigate the assumption of approximate normality and consider transformations (e.g., log) as needed. We will assess the functional form of time to account for any non-linear temporal trends and consider transformations as needed. Comparisons of the change from baseline to each time point between conditions will be performed using model-based linear contrasts. Data will be disaggregated by age, sex, and race to allow for analysis of each as biological variables.

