#### 10.1.6 SAFETY OVERSIGHT

Safety oversight will be under the direction of a PI. Aggregate reviews will occur by the PI for all AEs, UPs, protocol violations, audit results, early withdrawals, whether the study accrual pattern warrants continuation/action, and endpoint data. Aggregate reviews will occur monthly.

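### The primary BIS comparison is sized at two-sided 0.10 (Section 9.2) but tested at two-sided 0.05 (Section 9.4.1); at 0.05 no stated power figure is reached at its stated effect size

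*Combined protocol and SAP*

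**What the plan says.** Section 9.2 (Sample Size Determination) bases all its power statements for the primary endpoint on a two-sided two-sample t-test at 0.10 with 22 evaluable patients per arm. It claims "greater than 90% power for a standardized effect size of 0.93 and greater than 80% power for a standardized effect size of 0.78", and more than 80% power for a difference of 3.1 points with SD 4 or 5.5 points with SD 7. It presents the level as a choice: "Our selection of relaxed significance ( $\alpha = 0.1$ ) with maintained power", which "is based on the desire to emphasize power over type I error at this" early stage of development. The conventional level is assigned to the subsequent larger trial ("i.e. test BRIGHT with significance level of 0.05").

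Section 9.4.1 (General Approach) sets a different rule: "For inferential tests, we will use a p-value of 0.05, two-sided, and 95% confidence intervals (CIs) to assess statistical significance". It carves out no exception for the primary endpoint.

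Section 9.4.2 (Analysis of the Primary Endpoint) specifies a linear mixed effects model and says only: "Comparisons of the change from baseline to each time point between conditions will be performed using model-based linear contrasts". It names neither a significance level nor a confidence level. No other section reconciles the two.

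**The concern.** The rule that decides the primary comparison is not defined. An analyst working from Section 9.4 would test at 0.05 and report a 95% interval. A reader of Section 9.2 would expect 0.10. They disagree whenever p falls between 0.05 and 0.10, and that is the zone the relaxed level was chosen to capture, so that a promising intervention is carried forward to a larger trial.

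Timing adds to this. The trial is non-blinded (Section 4.1) and accrual is under way ("Our sample size is inflated by 20% based on interim accrual data"). The PI's aggregate reviews under Section 10.1.6 cover "whether the study accrual pattern warrants continuation/action, and endpoint data. Aggregate reviews will occur monthly". This does not show that anyone has seen BIS results by arm, and Section 9.4.6 plans no interim analysis. But a level left open now could later be chosen, or seem to have been chosen, with the results in view.

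**Working it through.** **Inputs, all from Section 9.2 unless noted.** 22 evaluable per arm, 1:1 (Section 6.3); two-sided two-sample t-test; standardized effects d = 0.78 and 0.93; 3.1/4 = 0.775; 5.5/7 = 0.786; planned mean changes 0.2 (control) and 4.6 (BRIGHT), difference 4.4; pooled SD 5.62, so 4.4/5.62 = 0.783.

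**Formula.** Degrees of freedom 2 × 22 − 2 = 42. Noncentrality δ = d × √(22/2) = d × √11. Power = 1 − F(t_crit; 42, δ) + F(−t_crit; 42, δ), where F is the noncentral t distribution function. The critical value t_crit is 1.682 at two-sided 0.10 and 2.018 at two-sided 0.05.

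**Step 1: reproduce the plan, then change only the level.**

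| Effect in Section 9.2 | Stated power | Power at 0.10 | Power at 0.05 |
|---|---|---|---|
| 3.1 / SD 4 (d = 0.775) | >80% | 81.2% | 70.9% |
| d = 0.78 | 80.2% (also >80%) | 81.6% | 71.5% |
| 5.5 / SD 7 (d = 0.786) | >80% | 82.1% | 72.1% |
| d = 0.93 | >90% | 91.8% | 85.4% |

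At 0.10 the claims reproduce. The stated 80.2% is 1.4 points below the 81.6% obtained here, a small gap that does not affect the argument. At 0.05 each figure falls below its stated threshold.

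The two levels cannot be reconciled by reading 0.05 as one-sided. That would give the same power as two-sided 0.10, but Section 9.4.1 says two-sided.

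**Step 2: detectable effect at 80% power, 22 per arm.** d = 0.762 at 0.10 and 0.865 at 0.05. Multiplied by 5.62, these are 4.28 and 4.86 BIS points, against a planned 4.4.

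**Step 3: observed differences that change verdict.** Standard error = 5.62 × √(2/22) = 1.694. The smallest significant difference is 1.682 × 1.694 = 2.85 points at 0.10 and 2.018 × 1.694 = 3.42 points at 0.05. An observed difference between 2.85 and 3.42 is significant under Section 9.2 and not under Section 9.4.1.

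**Step 4: how often that happens.** The probability that p lies between 0.05 and 0.10 is the difference of the two powers: 81.6 − 71.5 = 10.1% at d = 0.78; 91.8 − 85.4 = 6.4% at d = 0.93; and 5% under the null.

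**Step 5: sample size needed at 0.05.** d = 0.78 needs 27 evaluable per arm (54) for 80% power; d = 0.93 needs 26 per arm (52) for 90%. The plan has 44 evaluable and 52 enrolled. If all 52 were evaluable (26 per arm), power at 0.05 would be 78.2%, 78.8% and 79.3% for d = 0.775, 0.78 and 0.786. All three still fall short of 80%, while d = 0.93 would reach 90.8%.

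**The case against.** **The specific text governs the general.** Section 9.2 concerns the primary objective and argues for 0.10; Section 9.4.1 is a general approach. This is the likelier intention. But Section 9.2 is the sizing section, and the only level in the analysis sections is 0.05, stated without exception.

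**The power claims remain true.** They were computed at 0.10, so they stay correct as calculations whatever Section 9.4.1 says. That is fair: if 0.05 governs, they are not miscalculated, but they no longer describe the test that decides the trial.

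**The shortfall depends on the SD.** This is the strongest point. Section 9.2 also gives arm SDs of 5.9 and 3.9. Weighted equally, as 1:1 allocation implies, they pool to √((5.9² + 3.9²)/2) = 5.00, so d = 4.4/5.00 = 0.88. Power is then about 89% at 0.10 and 81% at 0.05 (81% also with Welch's test). On those inputs the trial passes 80% at either level. The plan, however, states its claims with 5.62. That value may be weighted by source sample size: 3.9 from the 9 pilot patients and 5.9 from an assumed 30 to 60 controls pool to 5.53 to 5.70, with about 42 giving 5.62. The control-source n is not in the documents.

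**The mixed model may be more efficient than a t-test.** Section 9.2 says so without quantifying it. At 0.05 the error variance of the contrast would have to fall by about 19% to restore 80% power at d = 0.78, or about 14% to restore 90% at d = 0.93.

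**It is a pilot with no go/no-go rule tied to p.** True, and the point estimate and data collection are unaffected. The trial still has a stated null hypothesis, a primary efficacy objective and a defended error rate.

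**Conclusion.** The concern holds. The contradiction is in the current text and depends on no assumption: the same primary result can be declared significant or not according to which section is followed. The loss of power is conditional. It arises only if 0.05 governs, and its size rests on the t-test with 22 per arm and the plan's own effect sizes. On that basis power drops by about 10 points for effects near 0.78 (to 71–72%) and by about 6 points at 0.93 (to 85%). It is smaller if the SD is nearer 5.00 or the mixed model brings a real gain. Because the level decides how the primary result is read, this needs correcting before any outcome analysis.

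**What to change.** Issue one dated amendment, before any outcome analysis, stating one significance level and the matching confidence level for the BRIGHT minus AC contrast in BIS change at 1 month. Sections 9.2, 9.4.1 and 9.4.2 should then agree. Two options:

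- **(a) Two-sided 0.10 with a 90% interval** for the primary contrast, keeping 0.05 and 95% for the other tests. This fits the rationale in Section 9.2. State also which level applies to the per-protocol analysis of the same endpoint (Section 9.3).
- **(b) Two-sided 0.05 with 95% intervals throughout**, with Section 9.2 restated at that level: about 71% power at d = 0.78, 85% at d = 0.93, and 80% at d = 0.865. The argument for a relaxed level would be removed.

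The amendment should record whether anyone choosing the level had seen BIS results by arm. It would also help to say how the pooled SD of 5.62 was derived; no replacement value is requested.

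The cost is a text amendment, with no additional patients and no change to data collection.
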